13.4 Early Stopping Rule

During Phase I CRM, the trial will stop if the posterior probability that the lowest dose is more toxic than the target is greater than 90%. Stopping rules will also be employed to monitor excess toxicity outside of the phase I trial. Stopping rule was developed using Pocock stopping boundaries [32]. The stopping rule will be monitored for Arm 1, 2A and Arm 2B separately.

Early Stopping Rule for Toxicity

Stopping rules were developed for excessive Grade 4/5 non-hematologic, non-infectious toxicity attributed to the study drug occurring by day 28 after the last dose of hCG. The goal is to construct a boundary based on toxicity such that the probability of early stopping is at most 10% if the toxicity rate is equal to 20% and assuming 13 more patients of each arm are enrolled after phase I. Given these parameters, the upper stopping boundary for toxicity is 2 events out of 2 patients, 3 events out of 3 patients, 5 out of 8, or 6 at any time. If the true toxicity rate is as high as 50% then chance of early stopping is 80% and the expected sample size is 7.3.

14 Conduct of the Study

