11.2 Adverse Event Documentation

Due to the complex medical condition of the post-transplant patient, monitoring for adverse events will focus on the following events beginning with the 1st dose of Pregnyl® and continuing for 4 weeks after the last dose. Any of these events will be documented on the study specific case report form:

- death
- anaphylaxis
- thromboembolic event
- Grade 3-4 skin injection site reaction
- Grade 3 headache
- Grade 3 gynecomastia
- Grade 3-4 ascites

In addition, the following events occurring by day 21 after the 1st dose of Pregnyl® are considered a dose limiting toxicity (DLT) and should be reported as such for patients enrolled in the Phase I component per [section 11.4](#):

- In males and females: Grade 2-4 thromboembolic event (CTCAE v4)
- In males and females: Grade 3-4 ascites (CTCAE v4)
- Specific to females: Grade 3-4 ovarian hyperstimulation syndrome, defined as the rapid development of enlarged, cystic, painful ovaries, Note: as there is no CTCAE grading for this event, the generic grading will apply as follows:

Grade	Description
1	mild; asymptomatic or mild symptoms; clinical or diagnostic observations
2	moderate; minimal or non-invasive intervention indicated

Grade	Description
3	severe or medically significant but not immediately life-threatening; hospitalization or prolongation of hospitalization indicated
4	life-threatening consequences; urgent intervention indicated

For the Phase II expansion cohort, an early study stopping rule was developed for excessive Grade 4/5 non-hematologic, non-infectious treatment probably or definitely attributed to the study drug occurring by day 28 after the last dose of Pregnyl® and is reportable per [section 11.4](#). Refer to [section 13.4](#) for details.

For both cohorts, relapse of the patient's malignancy and/or development of a new one occurring 4 weeks after the last dose is reportable per [section 11.4](#).

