The next cohort of 2 patients will not begin treatment until the last patient in the current cohort has reached day 21. Each new cohort of 2 patients will be assigned by the study statistician ([name] email: [contact]). The CRM assumes the working dose-toxicity model or power model. The probability (toxicity at d_i) = $p_i^{\exp(\alpha)}$ for each dose level i . The parameter α is distributed a priori as a normal random variable with mean 0 and variance 2. After simulation, a variance of 2 was predicted to balance both patient safety and accuracy. Pre-specified constants p_i for each dose are 1st determined by using the skeleton estimates at the beginning of the trial. After initiation of the trial and collection of events, the unknown parameter α is continuously updated. Calculation of posterior means of probability of toxicity from dose level i are calculated from Bayes theorem using the likelihood function based on a binomial distribution for the binary outcome of toxicity. After calculation of these means, each new cohort is assigned to the dose with an estimated toxicity probability closest to the pre-specified target toxicity of 25%.

Eventually the MTD will be identified when the total sample size of 20 patients is exhausted.

The dose limiting toxicity (DLT) is defined as any of the following occurring by day 21 after the 1st dose of hCG.

- In males and females: Grade 2-4 thromboembolic event (CTCAE v4)
- In males and females: Grade 3-4 ascites (CTCAE v4)
- Specific to females: Ovarian hyperstimulation syndrome, defined as the rapid development of enlarged, cystic, painful ovaries

Software within the BMA-CRMSimulator Version 2.1.0, downloaded from the MD Anderson biostatistics department website, will be used to calculate the posterior means of the toxicity probabilities for all of the doses under consideration:

<http://biostatistics.mdanderson.org/SoftwareDownload>. Dose escalation of more than one level is not permitted with this design.

Phase I component: Estimating the MTD of hCG for Arm 2B

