Dose	Actual probability in theory of having a DLT at each dose	Probability of Selecting the specified dose given the probabilities of having a DLT listed in the 2nd column	Estimated Number of subjects treated at each dose level during the study
125 USP hCG/875 pg EGF/m ²	0.25	0.28	6.7
250 USP hCG/1,750 pg EGF/m ²	0.30	0.29	3.1
500 USP hCG/3,500 pg EGF/m ²	0.40	0.23	5.3
1,000 USP hCG/7,000 pg EGF/m ²	0.50	0.07	2.6
2,000 USP hCG/14,000 pg EGF/m ²	0.60	0.02	0.7
3,500 USP hCG/24,500 pg EGF/m ²	0.70	0.00	0.2
5,000 USP hCG/35,000 pg EGF/m ²	0.75	0.00	0.1

Phase II extension: Studying the efficacy of hCG (Arm 1, Arm 2A and Arm 2B)

After completion of the dose finding trial for each arm, the final doses will be carried forward into a two-stage phase II extension trial to confirm safety and make a preliminary determination of the activity level for Arm 1 and Arm 2. If the phase I trial enrolls fewer than 13 patients at the MTD, we will employ Simon’s Minmax two-stage design (Simon, 1989) with the possibility to discontinue after the 1st stage if the response rate is low.

- **Stage 1:** Enroll a total of 12 patients (including all treated at the MTD in phase I). *If 5 or more of these respond, the trial will continue to stage 2.*

- **Stage 2:** Enroll an additional 14 patients. *If 14 or more out of 26 patients respond, hCG will be considered promising for further investigation.*

If phase I trial enrolls more than 12 patients at the MTD, we will adjust the futility rule above for the two stage design with the giving number of patients enrolled at the MTD.

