13.2 Sample Size Consideration

Resulting from laboratory studies conducted on the first several patients on this study, the investigative team plans to test higher doses in steroid-refractory patients with aGVHD (separating of Arms into 2A and 2B). This necessitates expanding the number of participants treated on the arms as described below:

Arm 1 Treated Patients	Arm 2A Treated Patients	Arm 2B Treated Patients
Level 1: N = 2, DLT = 0	Level 1: N = 1, DLT = 0	Level 1: N = 1, DLT = 0
Level 2: N = 2, DLT = 0	Level 2: N = 0, DLT = 0	Level 2: N = 2, DLT = 0
Level 3: N = 6, DLT = 0	Level 3: N = 3, DLT = 0	Level 3: N = 4, DLT = 0
Enroll 10 more patients Next dose level 3: N = 2	Enroll 16 more patients Next dose level 3: N = 2	Enroll 13 more patients Next dose level 4: N = 2

- The next dose was calculated with R package “dfcrm”.
- The next dose for Arm 2B was dose level 5, but restrict the dose jump, so the next dose will be dose level 4.

We now anticipate recruitment of 20 participants in each of the 3 arms to complete phase I.

In phase I, based on resources, the maximum number of allowable evaluable patients is 20 for each arm (total of 60 for all three arms). The simulations show it should be sufficient and safe to define the MTD for future efficacy trials.

For Arm 1 or 2A, if fewer than 13 patients are enrolled at the MTD, the phase II extension trial using Simon's two-stage Minmax design will require 26 patients to test the null hypothesis that the response rate at day 28 is <40% versus the alternative that the response rate is $\geq 65\%$ after assuming 80% power and a significance level of 0.05 and using a maximum of 26 patients. We will choose the rule that minimizes the expected sample size giving a true response rate equivalent to the null hypothesis. We expect that for each arm, phase I and II will require approximately 33 patients due to use of patients from the phase I trial in the phase II extension ([table 2](#) shows about 13 patients will be treated under MTD). But the sample size for each

arm could be as high as 44 when only two patients were treated at MTD in phase I. Therefore we expect the sample size of the phase I/II study for Arm 1 and Arm 2A will be 66 to 88 patients.

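### The Grade 4/5 toxicity stopping rule is sized for exactly 13 post-phase I patients in every arm, which the plan's own counts do not support, and it omits the phase I patients who are pooled into phase II

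*Combined protocol and SAP*

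**What the plan says.** Section 13.4 has two toxicity rules. During phase I the CRM stops the trial if the lowest dose is very probably too toxic. For the rest, "Stopping rules will also be employed to monitor excess toxicity outside of the phase I trial". Section 11.2 agrees on scope: "For the Phase II expansion cohort, an early study stopping rule was developed for excessive Grade 4/5 non-hematologic". This second rule counts Grade 4/5 non-hematologic, non-infectious toxicity attributed to the study drug, up to day 28 after the last dose, separately in each arm.

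Its design basis is that "the probability of early stopping is at most 10% if the toxicity rate is equal to 20" per cent, "assuming 13 more patients of each arm are enrolled after phase I". The method is given as "Stopping rule was developed using Pocock stopping boundaries". The printed boundary is 2 of 2, 3 of 3, 5 of 8, or 6 at any time. The claimed result at a 50% toxicity rate is an 80% chance of stopping and an expected sample size of 7.3.

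For efficacy, section 13.1 pools phase I and phase II: "Enroll a total of 12 patients (including all treated at the MTD in phase I"), followed by 14 more, 26 in all. The CRM counts three kinds of event (thromboembolic event, ascites, ovarian hyperstimulation) "occurring by day 21 after the 1st dose of hCG".

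**The concern.** There are two linked problems.

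**Coverage.** A phase I patient treated at the MTD contributes to the response count, but a Grade 4/5 drug-attributed event in that patient counts in no numerical rule unless it is one of the three DLT types and occurs by day 21. Responders may receive 10 maintenance doses twice weekly, starting on day 9 to 12 (Arm 1) or day 15 to 17 (Arms 2A and 2B). Part of that exposure falls after the DLT window closes. Phase II is described as confirming safety, so the events that bear on safety should be counted in the same patients.

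**Size.** A boundary of this kind has the stated error rates for one sample size only. With fewer new patients it has less power to stop. With more, it stops too often at an acceptable toxicity rate. Section 13.2 gives counts that differ from 13 in both directions, so the properties quoted to the oversight bodies may not be those of the rule in use.

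**Working it through.** **Method.** Exact binomial recursion, checked after every patient. A Pocock-type boundary stops at the smallest k for which P(X ≥ k | n, 0.20) ≤ c, with c chosen so that total stopping at a 20% rate is at most 10%.

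**Reproducing the plan's figures (13 patients).** The boundary is 2 events at n = 2, 3 at n = 3–4, 4 at n = 5–7, 5 at n = 8–11 and 6 at n = 12–13. It gives 9.7% stopping at 20% toxicity, and 79.7% with expected N 7.33 at 50%. These match the stated 10%, 80% and 7.3. The printed text omits the 4-event step. Read literally, it gives 6.6% at 20% and 74.2% at 50%, with expected N 8.7 to 8.8, even with 13 patients.

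**How many patients come after phase I (section 13.2).**
- Planning value for Arms 1 and 2A: about 13 at the MTD (Table 2), so 26 − 13 = 13 new. This agrees with the stated total of 33 = 20 + 13.
- Arm 1 status table: 6 at level 3 with no DLT, and 10 more to enroll, next at level 3 (the top level). 26 − (6 + 10) = 10 new.
- Arm 2A status table: 3 at level 3 with no DLT, and "Enroll 16 more patients", next at level 3. 26 − (3 + 16) = 7 new.
- Arm 2B planning value: about 9 at the MTD (Table 4). 26 − 9 = 17 new, which agrees with the stated total of 37 = 20 + 17.
- Any arm, worst case in section 13.2: 2 at the MTD. 26 − 2 = 24 new.

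To check the Arm 1 and 2A counts, the CRM was continued by simulation from the status table (power model, prior variance 2, target 25%). Even at the skeleton DLT rates it selects level 3 in about 99% (Arm 1) and 94% (Arm 2A) of runs, with means of about 16 and 18 patients there.

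**Stopping probability by number of new patients.** The full boundary is held at 6 events beyond n = 13.

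| New patients | Full, 20% rate | Full, 50% rate | As printed, 50% rate |
|---|---|---|---|
| 7 (Arm 2A) | 6.9% | 56% | 27–35% |
| 10 (Arm 1) | 8.1% | 69% | 50% |
| 13 (plan) | 9.7% | 80% | 74% |
| 17 (Arm 2B) | 15% | 94% | 93% |
| 24 (worst case) | 36% | 99.7% | 99.7% |

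The 27–35% range reflects whether 5 of 8 means five events at any point within the first eight patients, or only at the eighth.

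The Arm 2A figure can be checked by hand. At a 50% rate the full boundary can first be crossed at n = 2, 4, 6 or 7, with probabilities 0.25 + 0.125 + 0.0781 + 0.1094 = 0.5625.

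**A boundary for all 26 patients at the MTD.** The same method gives 3 events within 4 patients, 4 within 7, 5 within 10, 6 within 13, 7 within 17, 8 within 20, 9 within 24 and 10 within 26. Stopping is 9.6% at a 20% rate, 76% at 40% and 95% at 50% (expected N 9.8).

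**That boundary used alone.** After 19 event-free phase I patients, 7 new patients can reach at most 7 events, below the 8 needed by patient 20, so it cannot stop. After 16, all 10 new patients would need events: 0.5^10 = 0.1% at a 50% rate.

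**Both rules together.** Tracking both counts in one recursion (the 26-patient boundary, plus the full boundary on the last 10 or 7) gives false stopping at a 20% rate of about 16% (Arm 1) and 15% (Arm 2A).

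**The case against.** The strongest reply is that phase I patients are monitored. The CRM applies to them. Section 11.3 has affiliate sites report SAEs up to 4 weeks after the last dose within 24 hours, SAEs reach the DSMC under section 11.4, and section 12.3 requires quarterly progress reports. A reader might infer that these patients have no safety oversight, and the documents do not support that. What they lack is a pre-set Grade 4/5 boundary.

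A reader might also infer that most of the 26 in Arms 1 and 2A are certain to fall outside the rule. That needs level 3 to remain the MTD and the total to stay at 26. When more than 12 are at the MTD, the plan says only that the futility rule will be adjusted. On the Table 2 value the split is 13 and 13, and the stated 80% holds with the full boundary.

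Third, a reader might set 50% and 35% for Arms 1 and 2A against the stated 80%. That mixes two boundaries: the 80% belongs to the full one, and the lower figures to the printed shorthand, which gives 74% even with 13 patients. Like for like, the loss is about 11 points (80 to 69) in Arm 1 and 24 (80 to 56) in Arm 2A.

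None of this removes the mismatch. The 13 in section 13.4 is stated for each arm, while section 13.2 implies 17 for Arm 2B.

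**Conclusion.** The point holds in a conditional form and should be corrected. The Grade 4/5 rule excludes phase I patients who count for efficacy, and its stated properties are true only for 13 new patients and a boundary that is not fully printed. If level 3 stays the MTD and 26 stands, the chance of stopping at 50% toxicity is 69% in Arm 1 and 56% in Arm 2A, not 80%. In Arm 2B, on the plan's figure of about 9 at the MTD, false stopping at 20% toxicity is about 15%, above the 10% goal. In the worst case of 24 new patients it is about 36%. All figures assume a check after every patient and, beyond 13, that the limit of 6 events at any time is carried on. It would also be wrong to conclude that one pooled rule should replace the present one, since it would be nearly or wholly inert after a clean phase I.

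**What to change.** 1. Print the full boundary in section 13.4, including the 4-event step and the ranges of n to which each step applies.
2. When phase I closes in an arm, re-derive the boundary for the number still to be enrolled there, and restate stopping at 20% and 50% toxicity and the expected sample size. State whether the total remains 26 when more than 12 patients were treated at the MTD.
3. As a supplement, count Grade 4/5 drug-attributed events to 28 days after the last dose from the first patient treated at the MTD, against a 26-patient boundary such as the one under working. Keep the post-phase I rule beside it.

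No extra patients are needed, but there are two costs. The false-stop rate of the two rules together must be computed and stated. With the boundaries above it is about 15–16% at a 20% rate, so one or both would need tightening to hold 10%, with some loss of power. Grade 4/5 events and their attribution must also be captured for phase I patients at the MTD, because the section 11.2 form lists only targeted events, and SAE reports may need review to fill the gap.

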7.1 Arm 1 – High-Risk aGVHD

Standard of care immunosuppression, plus Pregnyl® (hCG supplementation) at assigned dose subcutaneously every other day for 4 doses

If a patient has a toxicity that fits the definition of dose limiting as defined in the phase I section below, the patient will discontinue study treatment.

Continue protocol treatment through day 7. Assess response at day 7:

- **If a complete or partial response**, the patient is eligible to receive Pregnyl maintenance at the same dose twice weekly for 10 doses beginning day 9 to 12. Refer to [section 9](#) for response definitions.
- **If no response**, the patient will be taken off study treatment

Pregnyl® dose level assignment will be done by treatment arm, with Arm 1 independent of Arms 2A and 2B.

For phase I, up to 5 dose levels of Pregnyl® will be tested; however dose levels -1 and -2 will be used only if dose level 1 proves too toxic.

Dose Level	Dose
-2	125 USP hCG/875 pg EGF/m ²
-1	250 USP hCG/1,750 pg EGF/m ²
1 (start)	500 USP hCG/3,500 pg EGF/m ²
2	1,000 USP hCG/7,000 pg EGF/m ²
3	2,000 USP hCG/14,000 pg EGF/m ²

The 1st 2 patients will be enrolled in dose level 1. The next cohort of 2 patients will not begin treatment until all patients in the current cohort have reached day 21 in order to assess for dose limiting toxicity (DLT).

Dose limiting toxicity (DLT) is defined as any of the following occurring by day 21 after the 1st dose of Pregnyl® (phase I component only):

- In males and females: Grade 2-4 thromboembolic event (CTCAE v4) i.e., any thrombosis more severe than a superficial venous thrombosis develops and treatment with anticoagulation is required
- In males and females: Grade 3-4 ascites (CTCAE v4)
- Specific to females: Grade 3-4 ovarian hyperstimulation syndrome, defined as the rapid development of enlarged, cystic, painful ovaries - refer to [section 11.2](#) for CTCAE grading guidance

Each new cohort of 2 patients will be assigned by the study statistician to the most appropriate dose level based on toxicity probabilities set for this study. The MTD will be identified when the total sample size of 20 patients is reached.

For the phase II the dose of Pregnyl will be that identified as the MTD during phase I.

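### Once phase I ends, the only arm-level toxicity boundary counts Grade 4/5 events, so the lower-grade dose-limiting events that set the MTD cannot trigger it.

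*Combined protocol and SAP*

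**What the plan says.** **Phase I.** Section 13.1 chooses the dose by CRM, with a target DLT rate of 25% in Arms 1 and 2A and 30% in Arm 2B. The DLTs are:

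- "In males and females: Grade 2-4 thromboembolic event (CTCAE v4")
- "In males and females: Grade 3-4 ascites (CTCAE v4")
- ovarian hyperstimulation, worded in 13.1 as "Specific to females: Ovarian hyperstimulation syndrome, defined as the rapid development of enlarged, cystic, painful ovaries" and in 11.2 as "Specific to females: Grade 3-4 ovarian hyperstimulation syndrome, defined as the rapid development of enlarged, cystic, painful ovaries"

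Sections 7.1-7.3 confine the definition to phase I: "occurring by day 21 after the 1st dose of Pregnyl® (phase I component only"). Section 11.2 has DLTs reported as such only for phase I patients.

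**Phase II.** The selected dose goes into "a two-stage phase II extension trial to confirm safety and make a preliminary determination of the activity level". Section 13.4 monitors toxicity outside phase I separately in each arm: "Stopping rules were developed for excessive Grade 4/5 non-hematologic, non-infectious toxicity attributed to the study drug", up to day 28 after the last dose. Section 11.2 describes the same rule with a narrower attribution: "an early study stopping rule was developed for excessive Grade 4/5 non-hematologic, non-infectious treatment probably or definitely attributed to the study drug". The boundary is 2 of 2, 3 of 3, 5 of 8, or 6 at any time. It was built for 13 further patients and at most 10% early stopping at a 20% rate.

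**What continues in phase II.** A DLT-type event ends that patient's study treatment (7.1-7.3, 7.5). Thromboembolic events and Grade 3-4 ascites go on the case report form for all patients (11.2). SAEs are reported (11.3, 11.4), and the DSMC receives quarterly reports (12.3).

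**The concern.** The events that decide the dose and the events that can stop an arm at that dose are defined differently. A Grade 2 or 3 thrombosis needing anticoagulation counts as a DLT in the last phase I patient. In the next patient, at the same dose, it counts toward no arm-level boundary. There is also a difference in attribution: the DLT definition has no attribution test, while the phase II rule requires one.

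At stake is the stated purpose of confirming safety. An MTD chosen from at most 20 patients may have a true DLT rate above target. An arm could then complete phase II and be called promising without its pre-specified toxicity rule ever having looked at most of the toxicity that defines the MTD.

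**Working it through.** **1. Definitions side by side.**

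| Event | Counts as DLT (13.1, 7.1-7.3, 11.2) | Counts in phase II rule (13.4, 11.2) |
|---|---|---|
| Thromboembolism | Grade 2-4 | Grade 4/5 if attributed; Grades 2-3 do not count |
| Ascites | Grade 3-4 | Grade 4/5 if attributed; Grade 3 does not count |
| Ovarian hyperstimulation | Grade 3-4 (7.1-7.3, 11.2) or no grade limit (13.1, schema) | Grade 4/5 if attributed; lower grades do not count |

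Ovarian hyperstimulation is also missing from the 11.2 list of events recorded for all patients.

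**2. The printed boundary.** I used an exact binomial recursion over 13 patients. With toxicity rate p and x events after n patients, P(n, x) = P(n−1, x)(1−p) + P(n−1, x−1)p, and a path is removed when it reaches a limit. Limits: 2 by patient 2, 3 by patient 3, 5 by patient 8, 6 at any time.

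- p = 0.20: stops with probability 0.066, so the 10% limit is met.
- p = 0.50: stops with probability 0.74, expected sample size 8.7. Section 13.4 states 80% and 7.3, so those two figures do not reproduce. That is a separate matter and does not affect this point.

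**3. What the rule sees at a true DLT rate of 50%.** The share s of DLT-type events that reach Grade 4/5 and are counted is not in the documents. I assume 0, 1/4 and 1/2, with no other counted toxicity. The counted rate is 0.50 × s.

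| s | Counted rate | Probability of stopping |
|---|---|---|
| 0 | 0 | 0 |
| 1/4 | 0.125 | 0.018 |
| 1/2 | 0.25 | 0.128 |

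**4. How likely is a dose above target?** In Table 3 the doses with true rates of 35%, 45% and 55% are selected with probability 0.22 + 0.09 + 0.01 = 0.32. In Table 5 the doses at 40%, 50% and 60% give 0.23 + 0.07 + 0.02 = 0.32. Both tables simulate excessively high toxicity. In Tables 2 and 4 no dose exceeds target, so the corresponding chance is 0.

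Section 13.2 reports 0 DLTs in 10 + 4 + 7 = 21 treated patients. The probability of seeing none under the pessimistic rates is:

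- Arm 1 (Table 3): 0.65² × 0.55² × 0.45⁶ = 0.001
- Arm 2A (Table 3): 0.65 × 0.45³ = 0.06
- Arm 2B (Table 5): 0.60 × 0.50² × 0.40⁴ = 0.004

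The pessimistic scenarios are thus unlikely at levels 1-3, with weaker evidence in Arm 2A. No patient had been treated at Arm 2B levels 4 or 5, which Table 4 selects with probability 0.14 + 0.78 = 0.92.

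**5. What a DLT-based boundary could do.** These are illustrations for 13 patients: stop when the binomial tail at the target is at or below a constant, chosen so that early stopping at the target is at most 10%.

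- Target 25% (3 of 3-4, 4 of 5-6, 5 of 7-9, 6 of 10-11, 7 of 12-13): stops with probability 0.09, 0.27 and 0.64 at true rates of 25%, 35% and 50%.
- Target 30% (3 of 3, 4 of 4-5, 5 of 6-8, 6 of 9-10, 7 of 11-12, 8 of 13): stops with probability 0.10, 0.26 and 0.50 at 30%, 40% and 50%.

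**The case against.** A severity-based rule in phase II is a legitimate choice, and the documents nowhere promise DLT monitoring there. The existing rule is broader than the DLT definition in two respects: it takes any attributed non-hematologic, non-infectious toxicity, and it runs to day 28 after the last dose instead of day 21 after the first. If other Grade 4/5 toxicity occurs, the stopping probabilities in step 3 are too low. This stands, and is why they are conditional on DLT-type events being the only source.

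A reader might infer that these events can never stop an arm. The documents do not support that. DSMC, IRB and sponsor oversight continues, an increased occurrence of serious suspected reactions goes to the FDA (11.4), toxicity proportions are reported per arm with confidence intervals (13.3), and attributed Grade 4 forms do count. What is true is narrower: the lower grades cannot trigger the pre-specified boundary, and none of the other safeguards states a criterion for acting on an arm.

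A reader might also take 32% as the chance that this trial carries forward a dose above target. It holds only in the pessimistic simulations, which the accumulated data make unlikely at levels 1-3.

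Finally, the added boundary has limited power against modest excess. At a true 35% (target 25%) or 40% (target 30%), where most of the 32% lies, the illustrations miss about three times in four. That stands, and must be disclosed with the boundary.

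**Conclusion.** The gap is in the text and does not depend on a calculation: after phase I, Grade 2-3 thromboembolism and Grade 3 ascites or ovarian hyperstimulation cannot trigger the only numerical arm-level toxicity rule, whatever their rate. It is a gap in the arm-level rule; individual discontinuation and routine safety reporting remain.

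Its size depends on the unknown share of DLT-type events that reach Grade 4/5. Over the assumed range of 0 to one half, the printed boundary stops an arm with a true 50% DLT rate at most 13% of the time. The practical exposure is greatest in Arm 2B, where levels 4-5 had no data and are the likely selection if the clinicians' estimates are right. Since phase II is meant to confirm safety, the plan should be amended. The change is a cheap improvement to monitoring, and does not imply that the current data show excess toxicity.

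**What to change.** 1. Reconcile the ovarian hyperstimulation grade between 13.1 and the schema on one side and 7.1-7.3 and 11.2 on the other, and the attribution wording between 13.4 and 11.2. Add ovarian hyperstimulation to the 11.2 list of events recorded for all patients.
2. Keep the Grade 4/5 rule. Add to 13.4, and to the Stopping Rule Event Form in 11.3, a second boundary per arm that counts DLT-type events by day 21 in patients enrolled after phase I. State in 7.1-7.3 and 11.2 that the definition applies to phase II for this count.
3. Use the arm's CRM target (25% or 30%) as the acceptable rate, with at most 10% early stopping. Calibrate to the number of new patients the arm may enrol. Under 13.2 this can reach 26 − 2 = 24 when only two patients were treated at the MTD, so the 13-patient limits above should not be adopted as they stand. The printed Grade 4/5 limits cannot be reused either: with all DLT-type events counted, they would stop 13% of the time at a 25% rate and 22% at 30%.
4. Report the boundary's stopping probabilities at the target and at modest and large excess.

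The cost is amendment wording, a recomputed boundary and one added event on the form. Sites must already recognise these events under 7.5. The statistical price is up to about a 10% chance of stopping an arm whose DLT rate equals the target.

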For Arm 2B, same as the other two arms, if fewer than 13 patients are enrolled at the MTD, the phase II extension trial using Simon's two-stage Minmax design will require 26 patients to test the null hypothesis that the response rate at day 28 is <40% versus the alternative that the response rate is $\geq 65\%$ after assuming 80% power and a significance level of 0.05 and using a maximum of 26 patients. We expect that for each arm, phase I and II will require approximately 37 patients due to use of patients from the phase I trial in the phase II extension ([table 4](#) shows about 9 patients will be treated under MTD). But the sample size could be as high as 44 when only two patients were treated at MTD in phase I. We expected the sample size of phase I/II study for Arm 2B will be 37 to 44 patients.

The number of evaluable patients per year will be approximately 20 for each arm. We expect accrual to be completed within 7 years.

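### The phase II toxicity boundary is built for 13 further patients in every arm; at the 17 expected in Arm 2B it stops falsely in 13 to 15% of cases if the arm enrols fully, against a stated limit of 10%

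*Combined protocol and SAP*

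**What the plan says.** Section 13.4 covers Grade 4/5 non-hematologic, non-infectious toxicity attributed to the study drug, in patients treated outside phase I. "Stopping rule was developed using Pocock stopping boundaries", with the aim that "the probability of early stopping is at most 10% if the toxicity rate is equal to 20% and assuming 13 more patients" follow; the design basis for the arms is "assuming 13 more patients of each arm are enrolled after phase I". The boundary is printed as "2 events out of 2 patients, 3 events out of 3 patients, 5 out of 8, or 6 at any time". Its power is given as: "If the true toxicity rate is as high as 50% then chance of early stopping is 80% and the expected sample size is 7.3". On scope: "The stopping rule will be monitored for Arm 1, 2A and Arm 2B separately".

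Section 13.2 sets phase I at 20 evaluable patients per arm and phase II at 26, counting phase I patients treated at the MTD. For Arms 1 and 2A it expects about 13 at the MTD and about 33 patients per arm. For Arm 2B it refers to Table 4, which "shows about 9 patients will be treated under MTD", and expects about 37 in total. Its upper case for Arm 2B reads "But the sample size could be as high as 44 when only two patients were treated at MTD in phase I"; the same maximum of 44 is given for each of Arms 1 and 2A.

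The only adaptation to the number at the MTD that the plan provides concerns the futility rule, when more than 12 patients were treated at that dose. Nothing adapts the toxicity boundary.

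**The concern.** A continuously monitored boundary has the stated error rate only for the number of patients it was built for. The last step here is a flat limit of six events with no upper patient count. In a longer series, six events accumulate by chance at a toxicity rate the plan treats as acceptable: at 20%, 13 patients yield 2.6 events on average, 17 yield 3.4 and 24 yield 4.8.

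Arm 2B is planned at 17 to 24 patients after phase I, a range that does not contain 13. The 10% limit is therefore stated for an arm whose planned size does not meet the condition attached to it. At stake is a false closure of Arm 2B for toxicity, and a committee judging a boundary crossing against the wrong error rate.

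**Working it through.** **Patients after phase I** (26 minus those at the MTD, or total minus 20)

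- Arms 1 and 2A, expected: 26 − 13 = 13; also 33 − 20 = 13.
- Arm 2B, expected: 26 − 9 = 17; also 37 − 20 = 17.
- Upper case, any arm: 26 − 2 = 24; also 44 − 20 = 24.
- Arm 2B from the counts in 13.2: 7 treated, none at level 5, 13 left, next 2 at level 4. At most 13 − 2 = 11 can reach level 5, so at least 26 − 11 = 15 follow if level 5 is chosen.

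**Method.** Exact recursion, patient by patient: after patient k with x events, stop if x reaches b(k); otherwise x grows by one with probability p. For a Pocock boundary, b(k) is the smallest x with P(Bin(k, 0.20) ≥ x) ≤ a, where a is the largest common level that keeps the total stopping probability at or below 10%.

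**Reproducing the plan's figures.** For 13 patients, a = 0.0504 and the boundary is 2 events at 2 patients, 3 at 3–4, 4 at 5–7, 5 at 8–11 and 6 at 12–13. All four printed points lie on it. It gives:

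- false stop at 20% toxicity: 9.7% (stated: at most 10%)
- stopping at 50% toxicity: 79.7% (stated: 80%)
- expected size at 50% toxicity: 7.33 (stated: 7.3)

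The four printed points alone give 74.2% stopping at 50%, so the full boundary is evidently the one intended. The printed list omits its four-event step.

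**The same rule with more patients**, the limit of six kept flat, p = 0.20:

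| Patients after phase I | Full boundary | Printed points only |
|---|---|---|
| 13 | 9.7% | 6.6% |
| 15 | 11.6% | 9.2% |
| 17 | 15.0% | 13.2% |
| 24 | 36.3% | 35.8% |

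**Allowing for the stage 1 futility stop** (fewer than 5 responses in 12), with toxicity and response assumed independent. With 9 at the MTD, 12 − 9 = 3 new patients precede that look, and the chance of a toxicity stop among them is 0.20² = 4.0%. The chance of a futility stop is 43.8% at a 40% response rate and 2.6% (0.0255) at 65%.

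- 40% response, full boundary: 0.438 × 0.040 + 0.562 × 0.150 = 10.2%. Printed points: 0.438 × 0.040 + 0.562 × 0.132 = 9.2%.
- 65% response, full boundary: 0.0255 × 0.040 + 0.9745 × 0.150 = 14.7%. Printed points: 13.0%.

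**The case against.** The strongest reply is that 13.4 contains no arithmetic error. The 10% limit is conditional on 13 patients, and under that condition every stated figure reproduces. This stands, and it rules out a reading that the rule fails in all arms: at their expected size, Arms 1 and 2A meet the limit.

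A reader might also infer that an arm would be wrongly closed about one time in three. The documents do not support that as an expectation. The 36% belongs to the upper case with two patients at the MTD, and 13.2 already records 6 patients at level 3 in Arm 1 and 3 in Arm 2A, with no DLT and level 3 next. Simulating the CRM onward from the recorded counts (skeleton taken as truth, phase I stop not modelled), two or fewer patients at the MTD occurred in under 1% of runs for Arm 1, about 3% for Arm 2A and about 1.4% for Arm 2B.

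The same simulation ended Arm 2B with 11 patients at the MTD, hence 15 to follow, in about 84% of runs. On current counts 15 is therefore likelier than 17, and at 15 the breach depends on the reading. That weakens the size of the point. It does not remove the mismatch, because 17 is the plan's own expected figure and the reading that matches its stated 80% and 7.3 exceeds 10% at 15 as well.

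Finally, the practical harm may be small. Section 2 puts severe reactions below 1%, and 13.2 shows no DLT in 10 + 4 + 7 = 21 patients (a different endpoint). At a true rate of 5% the present rule stops falsely in about 0.3% of cases at 17 patients; at 10%, in 1.4 to 1.7%. This is fair, but the plan chose 20% as its reference rate and states its guarantee there.

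**Conclusion.** The point holds for Arm 2B: the stated 10% limit does not carry over to the 17 patients that 13.2 expects after phase I. If the arm enrols to 26, the false-stop probability at 20% toxicity is 15.0%, or 13.2% with the printed points only. At 15 it is 11.6% or 9.2%. The limit also fails in any arm at the 24-patient extreme.

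Counting the futility stop, the 17-patient excess all but disappears for an inactive treatment (9.2 to 10.2% at a 40% response rate). It remains at 65% (13.0 to 14.7%), where a false closure costs most. These two ranges rest on independence of toxicity and response.

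A reader might infer that patients are less well protected than stated. The opposite is true: with more patients the rule stops more readily at every toxicity rate. The defect is a misstated false-stop probability for one arm, worth correcting before Arm 2B enters phase II.

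**What to change.** In 13.4, derive the Pocock boundary separately for each arm from the number actually left after phase I (26 minus patients at the MTD), at the same 20% rate and 10% limit. Print every step with its operating characteristics. Examples:

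| Patients left | Stop at | False stop at 20% | Stop at 50% | Expected size at 50% |
|---|---|---|---|---|
| 15 | 2 events within 2, 3 within 4, 4 within 7, 5 within 10, 6 within 14, 7 at 15 | 9.8% | 82.9% | 7.8 |
| 17 | 3 within 4, 4 within 7, 5 within 10, 6 within 13, 7 within 17 | 8.1% | 86.8% | 9.0 |
| 24 | as for 17, then 8 within 20 and 9 within 24 | 9.5% | 94.6% | 9.7 |

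The cost is a change of wording and no additional patients. The downside is that two events in the first two patients no longer trigger a stop at 17 or 24, although they still do at 15. Keeping that trigger at 17, by using the 13-patient steps and requiring 7 events for patients 14 to 17, gives 10.8%, slightly over the limit. If the sponsor prefers the present rule for its caution, 13.4 should state the higher false-stop probability for Arm 2B.
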